### 7.5.3.2 Reporting of (S)AEs - amended

The following events are to be reported to PPD on the SAE/ESI CRF within 24 hours of the investigator becoming aware of the event/diagnosis. Bayer HealthCare Pharmacovigilance is responsible for reporting these events to the health authority:

- Any non-cardiovascular death of a subject occurring after signing informed consent or prior to the end of monitoring for adverse events. (note: fatal bleeding events are primary safety outcomes and are exempted)
- Any non-cardiovascular SAEs not listed in Section 7.5.3.1
- Any non-cardiovascular AE that recurs when the subject is restarted on study drug (positive re-challenge).

In addition, any AEs of particular concern to the investigator may be recorded on the CRF to bring them to the attention of the sponsor.

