### **Long-Term Open-Label Extension – amended**

The safety collection requirements for the COMPASS trial will remain unchanged for the LTOLE.

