#### **7.5.1 E6 Definition of (serious) adverse event - amended**

An AE is any untoward medical occurrence including an exacerbation of a pre-existing condition or abnormal laboratory finding in a clinical investigation subject administered a pharmaceutical product and which does not necessarily have to have a causal relationship with this treatment.

A serious adverse event (SAE) is classified as any untoward medical occurrence that, at any dose, results in death, is life-threatening, requires inpatient hospitalization or prolongation of existing hospitalization, results in persistent or significant disability / incapacity is a congenital anomaly / birth defect and/or is another medically important serious event representing a significant hazard, which is comparable to the aforementioned criteria.

Note: If a subject is hospitalized or has a procedure that was planned or anticipated prior to the subject signing the informed consent, the hospitalization/procedure is considered part of medical history or a therapeutic intervention and is not the result of an (S)AE unless the severity has worsened or changed unexpectedly. Additionally, a procedure is not an (S)AE, but the reason for the procedure may be an (S)AE.

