#### **7.5.3 Protocol-specific adverse event definitions**

##### **7.5.3.1 Protocol-specific exceptions to SAE reporting - amended**

Rivaroxaban has been extensively studied in Phase 2 and 3 clinical studies involving more than 80,000^124 patients and its overall adverse event profile has been well described. Appropriate information concerning adverse events will be systematically collected and submitted to regulatory authorities and all data on safety and outcomes will be reviewed regularly by an unblinded Data and Safety Monitoring Board.

---

 Text added as per Amendment 11. (See Section 13.3.1)

 Text modified as per Amendments 6 and 8. (See Sections 13.1.2 and 13.2.2)

 Paragraph added with Amendment 8. (See Section 13.2.2)

 Section 7.5.2 and text within was added in Amendment 6.

For the purposes of this trial, the following events will be captured on the CRF as study outcome events only and will be waived from unblinding and will be exempted from the expedited reporting but will be included in the final study report.

- Primary efficacy outcomes:
  - Cardiovascular death
  - Myocardial infarction
  - Stroke
- Secondary and tertiary efficacy outcomes
  - Coronary heart disease death
  - Ischemic stroke
  - Acute limb ischemia
  - Cardiovascular hospitalization
  - Venous thromboembolism
  - Revascularization
  - Amputation
  - Stent thrombosis
  - Angina pectoris (unstable, worsening or new)
  - Heart failure
  - Resuscitated cardiac arrest
  - New diagnosis of cancer
  - Coronary artery bypass graft failure
- Primary safety outcomes:

As bleeding, including fatal bleeding, from all tissues and organs is a known side effect of rivaroxaban, bleeding events, including those resulting in hospitalization, will not be reported as (S)AEs, but will be captured on the CRF only, and will be reported as outcomes.

- Expected Events:

In addition, events that are expected to occur with high frequency in the population under study and for which no safety signal arose from more than 80,000 patients already studied in clinical trials with rivaroxaban will be captured on the CRF only, will be waived from unblinding, and will be exempted from expedited reporting. These include:

---

 Text modified/added as per Amendment 6. (See Section 13.1.2)

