#### 7.5.3.4 Non-serious adverse events

With the exception of the events of special interest defined in Section 7.5.3.3, AEs which are not serious but which lead to permanent discontinuation of study medication will be captured in the CRF but do not require expedited reporting.

Non-serious AEs which do not lead to discontinuation of study medication will not be collected.

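### A serious, non-fatal cardiovascular event that is not a listed outcome and causes no new admission has no mandatory SAE report, timeline or assigned form.

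*Protocol*

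**What the plan says.** Section 7.5.1 defines seriousness broadly. One criterion is that the event "requires inpatient hospitalization or prolongation of existing hospitalization"; threat to life, lasting disability and medical importance also count.

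Section 7.5.3.1 then takes events out of SAE reporting. It says that "the following events will be captured on the CRF as study outcome events only", and names efficacy outcomes that include cardiovascular death, MI, stroke, heart failure, angina, resuscitated arrest and cardiovascular hospitalization. Bleeding goes to outcome pages too. Two kinds of expected event are also exempt: planned admissions, and frequent non-cardiovascular conditions.

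Section 7.5.3.2 lists what must reach the coordinating centre on the SAE form within 24 hours:

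- "Any non-cardiovascular death of a subject occurring after signing informed consent or prior to the end of monitoring for adverse events"
- "Any non-cardiovascular SAEs not listed in Section 7.5.3.1"
- "Any non-cardiovascular AE that recurs when the subject is restarted on study drug (positive re-challenge")

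It adds that "any AEs of particular concern to the investigator may be recorded on the CRF".

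Section 7.5.4 sends the events of Sections 7.5.3.2, 7.5.3.3 and 7.5.3.5 to the SAE page and exempted outcomes to outcome pages. For the extension, Section 7.5 states: "The safety collection requirements for the COMPASS trial will remain unchanged for the LTOLE".

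**The concern.** An exemption from SAE reporting works if the exempted events and the reportable events together make up all SAEs. Here the two sides are drawn on different criteria. Section 7.5.3.1 exempts by a list of named events, while Section 7.5.3.2 requires by body system. A cardiovascular SAE that is not on the list satisfies neither.

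What is at stake is the route to pharmacovigilance. Section 6.5 provides for unblinding and reporting of suspected unexpected serious reactions, and the SAE page is the path by which Section 7.5.4 passes events to the sponsor. If a site follows Section 7.5.3.2 as written, an unexpected cardiovascular reaction outside the list is not sent down that path. Nor is an unlisted cardiovascular event that comes back when study drug is restarted. In LTOLE there is also no DSMB and no adjudication (Section 3.1).

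**Working it through.** No figure in the protocol is in question, so the check is to follow one test case through every route. The case is a non-fatal cardiovascular event that meets the Section 7.5.1 definition, is not a listed outcome and causes no new admission.

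| Route | Reaches the test case? | Reason |
|---|---|---|
| 7.5.3.1, outcome page | No | Not a named outcome; the cardiovascular hospitalization item, on its face, needs an admission |
| 7.5.3.1, expected events | No | The condition list is non-cardiovascular; the other item is planned admissions |
| 7.5.3.2, first bullet (deaths) | No | The case is not fatal; cardiovascular death is in any event an outcome, so this bullet leaves no gap |
| 7.5.3.2, second bullet (SAEs) | No | Non-cardiovascular only |
| 7.5.3.2, third bullet (re-challenge) | No | Non-cardiovascular only |
| 7.5.3.2, closing line | Optional | Permits recording, does not require it |
| 7.5.3.3 and Table 7-4 | Only if listed there | The cardiac row names one event, torsades de pointes |
| 7.5.3.4 | No | Deals only with non-serious events |
| Visit instructions in 7.1.2 | Yes, in general terms | Adverse events are to be recorded, but with no named form and no deadline |

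Two comparisons show that the gap is not explained by the protocol's own reasoning.

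1. *Definition against exemption.* Section 7.5.1 counts a new admission and a lengthened stay as alternative criteria. The broadest cardiovascular item in the outcome list uses only the word hospitalization. The plain reading leaves the lengthened stay uncovered.
2. *Rationale against scope.* Section 7.5.3.1 exempts events because they are captured as outcomes, because bleeding is a known effect, or because they are frequent and have raised no signal. An unlisted cardiovascular SAE meets none of these reasons.

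There is also an asymmetry with Section 7.5.3.4. A non-serious cardiovascular event that leads to permanent discontinuation must be captured on the CRF. Its serious, unlisted counterpart has no equivalent rule in Section 7.5.

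**The case against.** The strongest reply has four parts.

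*The events are still recorded.* Recording of adverse events is required at screening, randomization, clinic and telephone visits, the final visit, washout and LTOLE visits, with no cardiovascular exclusion. The only adverse events declared outside collection are these: "Non-serious AEs which do not lead to discontinuation of study medication will not be collected". A reader might infer from Section 7.5.3.2 that these serious events have no required record at all, or are lost. The documents do not support that. What the visit instructions do not supply is a deadline, a named form or a link to Section 7.5.4. That part of the point stands.

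*The residual is small.* The outcome list takes in nearly every major cardiovascular event, bleeding is captured separately, and torsades de pointes is a mandatory special-interest report. Table 7-4 also heads its entries as examples, so other cardiac events might be read into it. The first part is right and limits the point to a narrow set. The last is possible, but sites are given no other cardiac event to go by.

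*The hospitalization item may cover a prolonged stay.* The protocol does not define the term, and the Event Adjudication Plan is not at hand. Length of stay and intensive-care days are collected (Section 7.3), but for resource-use analysis. This may shrink the gap. It would not reach a life-threatening event managed without admission.

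*The restriction is deliberate.* Amendment 6 revised the safety section because outcomes were being misreported as SAEs. That justifies exempting listed outcomes, which the proposed wording keeps. It does not explain leaving out events that are not outcomes.

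**Conclusion.** The point holds in a limited form. Sections 7.5.1, 7.5.3.1, 7.5.3.2 and 7.5.4 do not fit together, and an unlisted, non-fatal cardiovascular SAE without a new admission, other than a Table 7-4 event, has no mandatory SAE report, timeline or assigned form. This rests on the plain reading of cardiovascular hospitalization as an admission and on treating Table 7-4 as naming the reportable cardiac events.

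The number of events cannot be derived from the protocol. A reader might point to the roughly 2,000 post-CABG subjects (2,000 / 27,400 = 7.3% of those randomized), who may still be in hospital at randomization, and attach a complication rate. An assumed 5% to 20% would give 100 to 400 events, but nothing in the document anchors either rate. The premise is also weak. Randomization comes at least 24 hours after chest-tube removal (Section 4.1.1), and the Amendment 8 rationale describes patients close to discharge. No count should be quoted.

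The consequence is incomplete expedited reporting of rare events. It does not affect the efficacy analysis or the primary bleeding outcome. Because the rivaroxaban/aspirin comparison has been stopped, a change now would act on the continuing pantoprazole comparison and on LTOLE.

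**What to change.** Define what is reportable as the complement of what is exempt.

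- Second bullet of Section 7.5.3.2: *Any SAE, cardiovascular or not, that is not listed as an outcome or expected event in Section 7.5.3.1.*
- Re-challenge bullet: *Any AE not listed in Section 7.5.3.1 that recurs when the subject is restarted on study drug.*
- State that both apply to LTOLE.

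The qualifier in the re-challenge bullet is needed. Simply deleting the restriction to non-cardiovascular events would demand 24-hour reports for listed outcomes, such as angina or heart failure, that recur after a restart. That would contradict Section 7.5.3.1, and interruptions and restarts are routine in this trial (Sections 6.4.1, 6.9.2 and 6.9.3).

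Section 7.5.4 already refers to Section 7.5.3.2, so the form and the deadline follow without further edits. All outcome, bleeding and expected-event exemptions remain. The cost is a short wording amendment, a note to sites and a small number of additional SAE pages.

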### 7.5.3.3 Adverse events of special safety interest - amended

For ongoing pharmacovigilance, the large COMPASS trial is an opportunity to identify rare events in the population that may or may not be drug-related. The following events have, to date, not been observed with increased frequency with rivaroxaban, but are considered AEs of special safety interest. These events must be reported to PPD independent of their seriousness, but within the same timelines as an SAE (within 24 hours) by reporting them on the SAE page of the CRF. Bayer HealthCare Pharmacovigilance may decide to upgrade the event based on the information received.

- Pregnancy outcome and any congenital anomaly
- Events currently under observation by Bayer HealthCare Pharmacovigilance and which may be unusual in the absence of drug therapy in the study population. The types of events that fall into this category are listed in Table 7-4.
- Events of special interest that are mild or moderate do not need to be reported in expedited fashion

---

 Text deleted as per Amendment 6. (See Section 13.1.2)

**Table 7–4. Adverse events of special interest**

| System Organ Class       | Example   |
|---------------------------------|--|
| Blood and lymphatic system      | Pancytopenia, aplastic anemia
Red cell aplasia
Agranulocytosis
Severe leukopenia
Severe neutropenia
Severe thrombocytopenia (<50 x 10  /L)
Thrombotic thrombocytopenic purpura
Immune thrombocytopenic purpura
Heparin-induced thrombocytopenia
Hemolytic anemia
Severe megaloblastic anemia
Disseminated intravascular coagulation |
| Skin and subcutaneous disorders | Severe exfoliative dermatitis
Severe bullous skin reactions
Erythema multiforme
Stevens Johnson Syndrome
Toxic epidermal necrolysis
Epidermolysis
Anaphylaxis
Angioedema requiring hospitalization
Angioneurotic oedema (not otherwise explained e.g. by ACE-inhibition)
Allergic vasculitis  |
| Hepatobiliary disorders         | Hepatic failure (incl. fulminant hepatitis, hepatic necrosis) and associated disorders (like hepatorenal syndrome, encephalopathy)
Severe hepatocellular damage and hepatitis
Jaundice (if unrelated to gallstones)  |
| Gastrointestinal disorders      | Pancreatitis
Retroperitoneal fibrosis
Pseudomembraneous colitis  |
| Renal and urinary disorders     | Acute nephritis (not caused by infection)
Nephrotic syndrome
Acute renal failure (only if not related to cardiovascular event or bleeding)   |
| Nervous system disorders        | Acute polyneuropathies   |
| Muscle disorders                | Rhabdomyolysis
Toxic myopathy   |
| Respiratory disorders           | Alveolitis
Acute interstitial pneumonia   |
| Infections                      | Severe sepsis  |
| Endocrine disorders             | Adrenal insufficiency
Addison's disease   |
| Eye and ear disorders           | Acute, sudden vision loss or acute reduced visual acuity (only if not related to stroke)
Sudden hearing loss  |
| Cardiac disorders               | Torsades de pointe   |

#### 7.5.3.4 Non-serious adverse events

With the exception of the events of special interest defined in Section 7.5.3.3, AEs which are not serious but which lead to permanent discontinuation of study medication will be captured in the CRF but do not require expedited reporting.

Non-serious AEs which do not lead to discontinuation of study medication will not be collected.

#### 7.5.3.5 Pregnancies - amended

The investigator must report to the sponsor any pregnancy occurring in a study subject, or in the study subject's partner, during the subject's participation in this study. The report should be submitted within the same timelines as an SAE, although a pregnancy per se is not considered an SAE.

For a study subject, the outcome of the pregnancy should be followed up carefully, and any outcome of the mother or the child should be reported. Abnormal pregnancy outcomes (eg, spontaneous abortion, stillbirth, and congenital anomaly) are considered serious adverse events and must be reported using the Serious Adverse Event Form. For the pregnancy of a study subject's partner, all efforts should be made to obtain similar information on course and outcome, subject to the partner's consent.

For all pregnancy reports, the forms provided by PPD are to be used.

#### 7.5.4 Reporting of events to Bayer by PPD and compliance with regulatory authorities' reporting requirements - amended

Adverse events that require expedited reporting described in Sections 7.5.3.2, 7.5.3.3, and 7.5.3.5 (protocol-specific adverse event reporting) are to be recorded on the appropriate SAE CRF page and are to be forwarded to PPD within 24 hours of the investigator having been made aware of the event. In this trial, exempted outcomes are to be recorded on the appropriate outcome CRF page, not the SAE CRF page. Upon receipt of an SAE CRF page this form will be reported to Bayer Global Pharmacovigilance by PPD within 24 hours, or 3 calendar days for weekends or public holidays, or next working day whichever is earlier.

All required information will be listed on the SAE page in the CRF. If the required information is not immediately available, PPD will query the center to obtain the information once it becomes available. In the rare circumstances that additional information is needed, PPD will work with Bayer and the site investigators to obtain additional information in a timely manner to enable Bayer to comply with regulatory authorities' reporting requirements.

#### 7.6 Other procedures and variables

No other procedures will be conducted and no other variables will be explored in this trial.

---

 Text modified/added as per Amendment 6. (See Section 13.1.2)

 Section 'Data Safety Monitoring Board' was deleted in Amendment 6. (See Section 13.1.2)

## **7.7 Appropriateness of procedures / measurements**

With the exception of routine laboratory assessments performed at screening, imaging studies performed in subjects randomized post CABG, and blood and imaging studies in those participating in the COMPASS MIND substudy, no invasive procedures are planned for this study. All study visits will be used to collect safety and outcome data, which are appropriate measures for this events-driven trial.

## **8. Statistical methods and determination of sample size**

### **8.1 General considerations**

General description of the statistical methods is outlined below. A more detailed statistical analysis plan (SAP) will be provided in a separate document.

The core SAP document will provide a more technical and detailed elaboration of the principal features of the planned analyses, e.g. censoring schemes for time-to-event variables. The core SAP will be finalized ideally prior to study enrollment, at the latest before any substantial information in the trial has accumulated.

Amendments and/or appendices to the core SAP will provide more details on the coding guidelines, data-handling, and output tables and figures. These SAP associated documents will be finalized ideally 6 months before planned study end to take into account emerging data external to the trial becoming available during conduct of the trial that could influence study interpretation. All SAP associated documents will be finalized without knowledge of any emerging results from the trial.

Analyses will be performed using SAS software (SAS Institute Inc, Cary, NC, USA).

### **8.2 Analysis sets and data scopes**

#### **8.2.1 Analysis sets**

##### **Intention-to-treat analysis set**

The intention-to-treat analysis set, also termed full analysis set in the International Conference on Harmonization (ICH) E9 guideline, will include all randomized subjects.

##### **Safety analysis set (for secondary safety analyses)**

The safety analysis set will include all randomized subjects who received at least one dose of study medication.

#### **8.2.2 Data scopes**

##### **Data scope according to intention-to-treat principle**

Analyses according to the intention-to-treat principle will be based on the intention-to-treat analysis set and will include all outcome events observed from randomization until the date of the Final Follow-up Visit for each subject. For subjects who are unable to attend the Final Follow-up Visit within the acceptable closeout time-window (range of dates depending on date of announcement of study termination), a calendar date will be chosen after which events will not be counted for primary analysis before unblinding. Subjects will be kept in the study

group to which they were randomized and the follow-up period for each subject will be as long and complete as possible.

### **Additional data scopes for secondary safety analyses**

Additional analyses of safety outcomes will be based on the safety analysis set. Subjects will be kept in the study group to which they were randomized. The outcome events will include:

- All outcome events observed from randomization until the date of the Final Follow-up Visit or a chosen calendar date described above for each subject
- All outcome events observed from randomization until 2 days following permanent discontinuation of the study drug (“treatment emergent outcomes” analysis)
- All outcome events observed from randomization up to 30 days following permanent discontinuation of the study drug
- All outcome events observed from randomization during the entire follow-up and wash-out periods

### **8.3 Variables – amended**

Time (in days) from randomization to the first occurrence of

- the primary, secondary, tertiary efficacy outcomes (except SAGE, MoCA, DSS, and EQ5D, and MRU) for the antithrombotic treatment randomization (Sections [8.3.1](#), [8.3.2](#), [8.3.3](#)),
- the primary safety outcome for the antithrombotic treatment randomization (Section [8.3.4](#)), and
- the outcome for the pantoprazole randomization (Section [8.3.5](#))

will be analyzed as time-to-event variables.

